### 2.14.2. **Secondary Endpoints**

Secondary endpoints in the study are as follows:

1. Reduction in fat layer thickness, as measured by ultrasound at Week 12 post-final treatment.
2. Subject satisfaction as assessed by Subject Self-Rating Scale scores.

## 2.15. **Statistical Analysis Plan**

### 2.15.1. **Statistical Methods: Overall Plan**

Data will be summarized based on the nature of the data. Dichotomous (e.g., gender, independent photographic review) and ordinal (e.g., Fitzpatrick Skin type) data will be tabulated by category. The mean, standard deviation, maximum, and minimum will be tabulated for continuous data (e.g., age, fat thickness). The significance level will be two-sided 0.05 for all statistical tests.

## 2.15.2. Analysis Population

Analysis Populations are defined as following:

Per-protocol Population (PP):

The Per-protocol Population will consist of all the treated subjects followed through to the final post-treatment visit and with weight change of no more than five percent at the time the final post-treatment visit images are taken. Since a weight change of more than 5 percent will affect the images, the primary Efficacy analysis will be performed based on this study population. Subjects who do not complete the treatment or had an interruption in the treatment will not be included in the primary and secondary Efficacy analyses.

As-Treated Population (AT):

This population consists of all treated subjects regardless of whether they become pregnant, undergo weight change during the study, or had interrupted treatment.

Safety Population (SA):

This population will consist of all the treated subjects with safety evaluation after the treatment. This population should be identical to the AT population. The safety data analyses will be performed based on the Safety Population.

## 2.15.3. Endpoint Analysis

### 2.15.3.1. Primary Safety Endpoint:

The primary safety endpoint is incidence of all device, drug – and/or procedure-related adverse events. All adverse events reported during and following the treatment will be included in the safety analysis. The frequency and proportion of subjects reporting each type of adverse event will be tabulated by relationship with the treatment and seriousness as well as severity of the event.

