Both CoolSculpting and KYBELL® are important treatment options for aesthetically-minded patients who are interested in reducing submental fat using minimally invasive interventions.

The purpose of this study is to evaluate the safety and efficacy of subcutaneous fat

ZELTIQ P/N: [REDACTED]  
Protocol Number: ZA17-005

This document and the contents hereof are considered proprietary and confidential information of ZELTIQ Aesthetics, Inc. Disclosure to unauthorized individuals or dissemination, publication or copying is prohibited without prior written consent of ZELTIQ.

reduction in the submental area in subjects initially with extreme submental fullness (Grade 4) based on the Clinician Reported-Submental Fat Rating Scale (CR-SMFRS), using sequential treatments of CoolSculpting (with the CoolMini applicator) and KYBELLA®.

[REDACTED]

[REDACTED]

[REDACTED]

[REDACTED]

In this study, subjects will receive two CoolSculpting treatments sessions each consisting of one cooling cycle with CoolMini, spaced 6 weeks apart, followed by at least one and up to two (2) KYBELLA® treatment sessions 6 weeks post the final CoolMini treatment, spaced 4-7 weeks apart.

After the completion of all treatment visits, subjects will be followed for 12 weeks post-final treatment. Safety information will be collected at study visits. Primary efficacy assessment will be evaluated at 12-weeks post-final treatment.

Results from this clinical trial will be used to provide feasibility data on the use of both CoolSculpting and KYBELLA® treatments sequentially to improve the treatment approach and availability for extreme submental fullness.

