**Figure 5. Subject enrollment and study flow.**

**Table 2. Schedule of assessments.**

	Screening (< 1 hr)	Treatment Visit 1 (< 3 hrs)	Treatment Visit 2 (< 3 hrs)	Treatment Visit 3 (< 3 hrs)	Treatment Visit 4 (Optional) (< 3 hrs)	2 Week Follow-Up (< 1 hr) †	Final Follow-Up (< 1 hr)
Time Frame	Day - 30 to 0	Day 0	6 ± 1 weeks post last tx	6 ± 1 weeks post last tx	4-7 weeks post last tx	2 weeks ± 3 days post each tx	12 ± 3 weeks post final tx
Informed Consent*	X						
Inclusion/Exclusion Criteria	X	X	X	X	X		
Pregnancy Test	X	X	X	X	X		
Medical History	X						
Tx Site Assessment	X	X	X	X	X	X	X
Oral Cavity Assessment	X		X	X	X	X	X
Nerve Function Assessment	X		X	X	X	X	X
Height	X						
Weight	X	X	X	X	X	X	X
CR-SMFRS Assessment	X			X	X		X
Photography	**X	X	**X	X	**X	**X	X
Ultrasound		X		X			X
CoolMini Treatment		X	X				
KYBELLA® Treatment				X	**X		
[REDACTED]		X	X	X	X	X	X
AE Assessment		X	X	X	X	X	X
Subject Self Rated Scale	X			X			X

\* Informed consent to be signed by subject prior to the collection of any data or completion of any study procedures.

\*\* Optional

† Follow-up after each treatment

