### **2.15.3.4. Secondary Endpoint: Subject Self-Rating Scale**

### **2.15.3.5. Sample Size Requirement**

Up to twenty (20) subjects is thought to be appropriate to provide feasibility information regarding safety and efficacy of submental treatment using CoolMini vacuum applicator and KYBELLA® sequentially.

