### **Reportable Incidents**

Serious adverse events (SAEs) and unanticipated adverse device effects (UADEs) must be reported within 24 hours of knowledge of the event to the Sponsor.

All adverse events observed by the investigator or reported by the subject will be recorded on the appropriate CRF, irrespective of relationship to CoolSculpting and KYBELLA®, as well as the KYBELLA® skin grid. Medically significant adverse events will be followed until resolved or considered stable. For each event, the investigator will record a description, dates of onset and resolution, severity, and relationship to CoolSculpting, KYBELLA® and KYBELLA® skin grid. The investigator may be required to provide follow-up information.

Any adverse event that results in withdrawal from the study must be reported to the Sponsor after the decision to withdraw the subject is made.

Any death occurring during the study must be reported to the Sponsor within 24 hours of the discovery of the event. This includes any death that occurs within 30 days after the subject's final visit, irrespective of when the final visit occurs.

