### Assessment of Causality

- The investigator is obligated to assess the relationship between study treatment and each occurrence of each AE/SAE.
- A *reasonable possibility* of a relationship conveys that there are facts, evidence, and/or arguments to suggest a causal relationship, rather than a relationship cannot be ruled out.
- The investigator will use clinical judgment to determine the relationship.
- Alternative causes, such as underlying disease(s), concomitant therapy, and other risk factors, as well as the temporal relationship of the event to study treatment administration will be considered and investigated.
- The investigator will also consult the investigator's brochure and/or product information, for marketed products, in his/her assessment.
- For each AE/SAE, the investigator must document in the medical notes that he/she has reviewed the AE/SAE and has provided an assessment of causality.
- For each AE/SAE, there are 5 levels of causality, as follows:
  - Not related
  - Unlikely
  - Possible
  - Probable
  - Causal relationship

- There may be situations in which an SAE has occurred and the investigator has minimal information to include in the initial report to the sponsor. However, it is very important that the investigator always make an assessment of causality for every event before the initial transmission of the SAE data to the sponsor.
- The investigator may change his/her opinion of causality in light of follow-up information and send an SAE follow-up report with the updated causality assessment.
- The causality assessment is one of the criteria used when determining regulatory reporting requirements.

The investigator will determine the relationship of each adverse event to CoolSculpting and/or KYBELLÀ® using the question: "Is there a reasonable possibility that the event may have been caused by treatment with CoolSculpting and/or KYBELLÀ®? Answer 'yes' or 'no' for each adverse event."

The guideline below should be used to consider relatedness:

For a "no causal relationship" assessment, the adverse event:

- May be judged to be due to extraneous causes such as disease or environment or toxic factors
- May be judged to be due to the subject's clinical state or other therapy being administered
- Is not biologically plausible
- Does not reappear or worsen when CoolSculpting and/or KYBELLÀ® is re-administered
- Does not follow a temporal sequence from treatment with CoolSculpting or administration of KYBELLÀ®

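### The adverse-event table pools up to four sessions over all treated subjects, so it dilutes post-KYBELLA proportions and cannot describe safety after each step of the sequence

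*Combined protocol and SAP*

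**What the plan says.** **Analysis.** Section 2.15.3.1 states that "All adverse events reported during and following the treatment will be included in the safety analysis". It then plans the number and proportion of subjects with each event type, "tabulated by relationship with the treatment and seriousness as well as severity of the event". No visible text adds session, product phase or time since the last treatment.

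**Denominator.** Section 2.15.2 bases the safety analysis on all treated subjects with a safety evaluation. Under Section 2.10 a subject is enrolled once the first cooling begins. No KYBELLA-exposed population is defined.

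**Exposure.** Section 1.1 describes two CoolMini sessions, "followed by at least one and up to two (2) KYBELLA® treatment sessions 6 weeks post the final CoolMini treatment". Section 2.11.3, however, sends only subjects scored 3 or 2 on the CR-SMFRS on to KYBELLA, and Section 2.11.4 makes the second KYBELLA session optional.

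**Data collected.** For each event the investigator records "dates of onset and resolution, severity, and relationship to CoolSculpting, KYBELLA® and KYBELLA® skin grid" (Section 2.18, Reportable Incidents). Table 2 and Section 2.12.1 place a safety visit at "2 weeks ± 3 days post each tx".

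**Aim.** Section 2.15.3.5 justifies the sample as giving feasibility information on "submental treatment using CoolMini vacuum applicator and KYBELLA® sequentially".

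**The concern.** For a study of two products given in sequence, the basic safety description is what happened after each step and in how many of the subjects who took that step. The planned table has no time axis, so an event after the first cooling and an event after an injection into twice-cooled tissue enter the same row. A subject with the same event after one session and a subject with it after every session are each counted once.

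The denominator adds a second problem. Events that begin after KYBELLA can occur only in injected subjects, yet they are divided by everyone who was cooled. The resulting proportion cannot be set beside the KYBELLA rates that Section 6.2 quotes, which are among KYBELLA-treated subjects. Those are the only reference rates in the documents.

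**Working it through.** The plan gives no event rate, target precision or power for its maximum of 20 subjects, so it has no figure of its own to reproduce. The checks below concern what pooling does and what the extra table could deliver.

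**1. Dilution by the denominator.** Let N be all treated subjects, n the number injected and p the event rate among those injected. Events with onset after KYBELLA contribute p × n/N to the pooled proportion. Take N = 20. For p, use two rates from Section 6.2 purely as reference values: 72% (injection-site hematoma/bruising) and 42% (numbness lasting more than 30 days). The number injected is not known in advance, so n is varied as an assumption.

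| Injected (n) | p = 72% | p = 42% |
|---|---|---|
| 20 | 72% | 42% |
| 15 | 0.72 × 15/20 = 54% | 0.42 × 15/20 = 31.5% |
| 10 | 0.72 × 10/20 = 36% | 0.42 × 10/20 = 21% |

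There is no dilution if all 20 are injected. For the optional second KYBELLA session, n can be smaller again. Events of the same type that begin after CoolSculpting push the pooled figure up, so the total may lie below or above the post-KYBELLA rate. The table does not show which.

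**2. Pooling over sessions.** If each session carried risk q, independently (an assumption), the proportion with at least one event over four sessions would be 1 − (1 − q)^4. For q = 10% this is 1 − 0.9^4 = 34%, and for q = 20% it is 1 − 0.8^4 = 59%. Neither can be read back as a per-session rate. At most 20 × 4 = 80 session follow-ups reduce to 20 subject-level entries per event type.

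**3. Can the relationship split stand in?** In part.
- Section 2.18 (Reportable Incidents) records relationship to each product, so a product split is possible.
- Section 2.15.3.1 says relationship with the treatment and does not say by product.
- Under Assessment of Causality the wording is joint: "The investigator will determine the relationship of each adverse event to CoolSculpting and/or" KYBELLA, with a yes/no answer. The same part of the protocol also lists five causality levels.
- Attribution to a product cannot separate CoolSculpting 1 from CoolSculpting 2, or KYBELLA 1 from KYBELLA 2. Onset date can.

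**4. What a by-session table could show.** Exact (Clopper-Pearson) 95% limits are wide. With 0 events the upper limit is 1 − 0.025^(1/n): 16.8% for 0 of 20 and 30.8% for 0 of 10. For 15 of 20 the interval is 51% to 91%.

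The next table tests a post-KYBELLA rate against a fixed quoted rate, by an exact test with upper tail at most 0.025 and all 20 injected.

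| Reference rate | Events needed | True rate for 80% power |
|---|---|---|
| 72% | at least 19 of 20 | about 96% |
| 42% | at least 14 of 20 | about 76% |
| 20% (prolonged swelling, Section 6.2) | at least 9 of 20 | about 52% |

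If only 10 are injected, even 10 of 10 does not exceed 72% at this level, since 0.72^10 = 0.037. The table's value is therefore descriptive.

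**5. Interval lengths (Table 2).** The interval is 5 to 7 weeks after each CoolSculpting session, 4 to 7 weeks after KYBELLA 1 if a second follows, and 9 to 15 weeks after the last session. KYBELLA 1 falls 10 to 14 weeks after CoolSculpting 1 (two gaps of 6 ± 1 weeks). Section 6.2 says paradoxical hyperplasia may develop 2 to 5 months after treatment, so a late CoolSculpting effect can begin inside a KYBELLA interval.

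**The case against.** The strongest reply has four parts.

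- **Design limits.** A reader might infer that pooling is what stops the study from showing that prior cooling raises KYBELLA event rates. The documents do not support that. Every subject follows the same order, no KYBELLA-only group is described, and there are at most 20 subjects on a feasibility rationale. No table would change this. The objection stands in full.
- **The split is not absent.** Relationship is recorded for CoolSculpting, KYBELLA and the skin grid, so some separation by product is available. This stands, but the analysis section does not commit to it and it cannot separate sessions of the same product.
- **The columns would not be like for like.** Section 6.2 does not count anticipated CoolSculpting effects as adverse events, including mild to moderate transient bruising and swelling. No matching exclusion is stated for KYBELLA. A rise from CoolSculpting to KYBELLA columns could be purely definitional, and a reader might wrongly take it as evidence of increasing harm. Unequal intervals and late-onset events add to this. These cautions stand and belong on the table itself.
- **Nothing is lost.** The data are kept and the plan does not forbid the table. True, but without prespecification its production, denominators and windows are left to choice after the data are seen.

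**Conclusion.** The point holds as an omission in the analysis of a primary endpoint. The planned table cannot describe event rates after each step of the sequence. It also dilutes post-KYBELLA proportions by the factor n/N whenever some subjects are not injected: with an assumed rate of 72%, to 54% at 15 of 20 and to 36% at 10 of 20. The size depends on how many subjects reach KYBELLA, which the documents do not predict, and dilution vanishes if all do. The lack of a step-by-step description does not depend on that number.

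The conclusion goes no further. The overall incidence is a legitimate primary result, and a by-session table would supplement it with description only.

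**What to change.** Keep the overall incidence as primary and add to Section 2.15.3.1, for example:

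> Adverse events will also be summarised descriptively by the last session before onset (CoolSculpting 1, CoolSculpting 2, KYBELLA 1, KYBELLA 2), as number and proportion of the subjects treated at that session, with exact 95% confidence intervals. A subject with repeat occurrences is counted in each interval in which one begins. Relationship to each product is shown alongside. Interval lengths are reported.

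Restricting the summary to a common window after each session, such as up to the 2-week visit, is an alternative to reporting unequal intervals.

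Add a footnote that anticipated CoolSculpting effects (Section 6.2) are not counted as adverse events, so columns for the two products are not directly comparable, and that late-onset effects may fall in a later session's interval. State that the table is not intended to test whether prior cooling changes KYBELLA event rates.

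**Cost.** One extra table from data already collected, with no new visits or subjects. The downside is a table whose columns can be over-read across products, which is why the footnote should be part of the specification.

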### **2.15.3.2. Primary Efficacy Endpoint: Reduction in CR-Submental Fat Rating Scale**

The primary efficacy endpoint is the change in subcutaneous fat layer in the submental area as measured between the baseline and final post-treatment visit CR-Submental Fat Rating Scale scores. Since weight change may affect the fat layer thickness, the analysis will be based on the evaluation of the PP population, i.e. treated subjects followed through to the final post-treatment visit who did not become pregnant, and with weight change of no more than 5 percent at the final post-treatment visit.

### **2.15.3.3. Secondary Endpoint: Ultrasound**

A secondary efficacy endpoint is the change in subcutaneous fat layer as measured between the pre- and final post-treatment visit images. Since weight change may affect the fat layer thickness, the analysis will be based on the evaluation of the PP population, i.e. treated subjects followed through to the final post-treatment visit who did not become pregnant, and with weight change of no more than 5 percent at the final post-treatment visit.

### **2.15.3.4. Secondary Endpoint: Subject Self-Rating Scale**

### **2.15.3.5. Sample Size Requirement**

Up to twenty (20) subjects is thought to be appropriate to provide feasibility information regarding safety and efficacy of submental treatment using CoolMini vacuum applicator and KYBELLA® sequentially.

## **2.16. Missing Data Handling**

In general, no imputation for missing data will be made. Data will be analyzed “as-is” where subjects with missing data not being included in the analysis.

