## 2.6. ***Sample Size***

A maximum of twenty (20) subjects will be treated at up to three (3) investigational sites.

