All subjects will be asked to maintain their weight by not making any major changes to their diet or exercise regimen during the course of the study. If the weight change is more than 5% at the final visit, the subjects' data will be excluded from the primary Efficacy analyses. Subjects who do not maintain their weight within 5% will continue in the study, however their data will be excluded from Efficacy analyses.

Subjects who meet all of the inclusion criteria and none of the exclusion criteria shall be eligible to participate in the study and the first treatment will be scheduled.

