### 2.14.1. **Primary Endpoints**

The primary endpoints of the study will be defined as follows:

- Safety endpoint: incidence of device, drug or procedure-related adverse events.
- Efficacy endpoint:
  1. The reduction, from baseline (CR-SMFRS =4) to final follow-up, of submental fat (SMF) as assessed by the proportion of subjects who have at least a 1-grade improvement on the Clinician Reported Submental Fat Rating Scale (CR-SMFRS), and
  2. The reduction, from baseline (CR-SMFRS=4) to final follow-up, of SMF as assessed by the proportion of subjects who have at least a 2-grade improvement on the CR-SMFRS.

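### The primary responder proportions describe only Per-protocol completers, and no all-treated efficacy analysis is assigned to show what the exclusions do

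*Combined protocol and SAP*

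**What the plan says.** Section 2.14.1 defines two primary efficacy measures: the proportions of subjects improving by at least one grade and by at least two grades on the CR-SMFRS, from baseline to final follow-up. Sections 2.15.2 and 2.15.3.2 analyse these in the PP set, which needs a completed final visit and a weight change within 5% at that visit. Section 2.15.2 also takes subjects with unfinished or interrupted treatment out of the primary and secondary efficacy analyses, and 2.15.3.2 takes out pregnancies. Section 2.16 makes no imputation in general and works on complete cases, "where subjects with missing data not being included in the analysis".

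Section 2.9.1 states the weight rule twice. First: "If the weight change is more than 5% at the final visit, the subjects' data will be excluded from the primary Efficacy analyses". Then: "Subjects who do not maintain their weight within 5% will continue in the study, however their data will be excluded from Efficacy analyses". Only the first sentence limits the rule to the final visit and to the primary analysis.

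Section 2.15.2 also defines an As-Treated set: "This population consists of all treated subjects regardless of whether they become pregnant, undergo weight change during the study, or had interrupted treatment". In the visible text of 2.15.3.1 to 2.15.3.3, safety goes to the Safety Population and efficacy to PP. Section 2.15.3.4 shows no text, so the statement that As-Treated has no efficacy analysis rests on what can be read.

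**The concern.** The visible text describes one treatment sequence and no comparator, so the responder proportion is the main efficacy answer. A reader will take it as the chance that a subject who starts the sequence improves. What the plan produces is the chance among subjects who finished treatment without interruption, returned for the final visit and kept their weight.

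The two differ whenever the excluded subjects respond at another rate than those who stay. Sections 2.11.1 and 2.11.3 allow treatment to be stopped for discomfort, so poor tolerability can itself remove a subject from the efficacy result. Subjects over the weight limit raise a separate issue: their final CR-SMFRS is collected under 2.12.2 and then not used. With at most 20 subjects, each one is worth 1/20 = 5 percentage points of an all-treated proportion.

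**Working it through.** **Inputs from the documents.** N = 20 is the ceiling: "A maximum of twenty (20) subjects will be treated at up to three (3) investigational sites". No response rate, dropout rate, power or precision target is given, so the sample size cannot be re-derived and is not called wrong here. The numbers excluded and improved below are assumptions.

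**Formulas.** Let m be the number excluded, x the number improved among the N − m in PP, and r the unknown number improved among the excluded.

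- PP proportion = x/(N − m)
- All-treated proportion = (x + r)/N, from x/N at r = 0 to (x + m)/N at r = m
- The two agree when r = m·x/(N − m)

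**Bounds.**

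| Excluded | PP | All treated, r = 0 | All treated, r = m |
|---|---|---|---|
| 4 of 20 | 13/16 = 81.3% | 13/20 = 65.0% | 17/20 = 85.0% |
| 2 of 20 | 15/18 = 83.3% | 15/20 = 75.0% | 17/20 = 85.0% |

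**Direction.** In the first row, r = 0, 1, 2, 3, 4 gives all-treated 65%, 70%, 75%, 80%, 85%. PP less all-treated (from 81.25%) is +16.25, +11.25, +6.25, +1.25 and −3.75 points. The break-even is r = 4 × 13/16 = 3.25. PP overstates if the excluded respond less often than the completers and understates if they respond more often.

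**What an all-treated analysis would report.** Split m into w subjects with a final score (over the weight limit, or interrupted) and u with none. Using observed scores and counting missing scores as not improved gives (x + r_w)/N, where r_w is the number improved among the w; the best case adds u/N. In the first row:

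- All four unscored: 65%, best case 85%.
- All four scored: the observed value, somewhere between 65% and 85%.
- Two of each: 13/20 to 15/20, so 65% to 75%, with a best case 2/20 = 10 points higher.

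**A response-linked route out of PP.** All subjects enter at grade 4 (Table 1). Section 2.11.3 moves those scored 3 or 2 at Visit 3 to the drug phase, and 2.15.2 excludes those who do not complete treatment. The documents do not say how a subject who does not move on is classified. Suppose k subjects stay at grade 4, are dropped as non-completers, and everyone else improves. PP then shows 100%, while all-treated is 18/20 = 90% for k = 2 and 16/20 = 80% for k = 4. Dropping subjects already at grade 1 or 0 would act the other way.

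**The weight rule.** Sections 2.15.2, 2.15.3.2 and 2.15.3.3 all assess weight at the final visit, and 2.15.3.3 applies the limit to the secondary ultrasound endpoint as well. In 2.9.1 the first sentence has that timing but covers only the primary analysis; the second covers efficacy generally but gives no timing. Weight is recorded at every visit (Table 2). Read literally, a subject 6% up at Visit 3 and back within 5% at the end is kept by the first sentence and excluded by the second. No section names the reference weight, although weight is taken at both Screening and Day 0.

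**The case against.** This is a feasibility study: "Up to twenty (20) subjects is thought to be appropriate to provide feasibility information regarding safety and efficacy". The plan sets an alpha ("The significance level will be two-sided 0.05 for all statistical tests") but names no test or null rate for the primary endpoint, so no formal decision turns on the denominator. The weight exclusion is prespecified with a reason, that weight change affects the measurement. Sampling error is also large: with an assumed 12 of 16, the exact 95% interval is 47.6% to 92.7%, wide enough to contain the shifts shown above. All of this stands. It supports keeping PP as primary and limits how serious the point is. It does not make a completer proportion describe all treated subjects, and the interval does not reflect selection.

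It can also be said that the 2.9.1 sentences barely conflict. The second follows directly on one that sets the timing, and three SAP sections agree on the final visit. That largely stands: the intended timing is clear, and what is needed is a wording correction.

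A reader might infer that the reported response is likely overstated. The documents do not support that for the exclusions as a whole. Leaving for lack of effect or discomfort makes it plausible for withdrawals and non-completers. The weight rule, however, removes losers as well as gainers; dropping those who lost weight may remove responders and lower the PP rate. No expected counts are given from which to judge the net effect.

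**Conclusion.** The point holds as a gap in the analysis plan. Both primary proportions are completer figures, final scores from subjects over the weight limit are collected without a visible efficacy use, and the set that would retain these subjects has no efficacy analysis assigned. The result may be biased. Overstatement is plausible for withdrawals and treatment non-completers; for weight exclusions the direction is unknown.

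Under the assumed counts, PP of 81% sits against 65% to 85%, and PP of 83% against 75% to 85%. A reader might take 65% or 75% as the corrected rate. Each is only the lower bound, reached if none of the excluded subjects improved. A reader might also infer that assigning efficacy to As-Treated is enough. It is not, because 2.16 would still drop anyone without a final score.

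This should be corrected, but in a small feasibility study it does not invalidate the design.

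**What to change.** - **2.15.3.2:** keep PP as primary. Add that both responder proportions are also reported for all treated (As-Treated) subjects, using the observed final CR-SMFRS regardless of weight change or treatment interruption, counting subjects with no final score as not improved, and showing the best-case bound alongside.
- **2.16:** state this as an exception to the no-imputation, complete-case rule; otherwise the two sections conflict.
- **Listing:** give each subject excluded from PP, with the reason and last CR-SMFRS score. Section 3.4.3 already has monitors check that reasons for non-completion are recorded.
- **2.9.1:** reword the second weight sentence so that the exclusion is assessed at the final visit and covers the PP primary and secondary efficacy analyses, matching 2.15.2, 2.15.3.2 and 2.15.3.3. Keep the provision that these subjects remain in the study. State whether the Screening or the Day 0 weight is the reference.
- **2.11.3 and 2.15.2:** reconcile these on whether a subject who does not move to the drug phase counts as having completed treatment. The all-treated table includes such subjects either way.

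The cost is SAP wording, one extra table and one listing, all from data already collected. The downside for the sponsor is that the all-treated rate will usually be lower than the PP rate, since missing scores count as not improved.
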